4.3. Study Termination

The investigator retains the right to terminate study participation at any time, according to the terms specified in the study contract. The investigator is to notify the IRB/IEC of the study's completion or early termination in writing, send a copy of the notification to the sponsor or sponsor's designee, and retain 1 copy for the site study regulatory file.

The sponsor may terminate the study electively or if required by regulatory agency. In the event of significant safety findings, the study will be terminated. If the study is terminated prematurely, the sponsor will notify the investigators, the IRBs and IECs, and regulatory bodies of the decision and reason for termination of the study.

5. STUDY POPULATION

Deviations from eligibility criteria are not allowed because they can potentially jeopardize the scientific integrity of the study, regulatory acceptability, and/or participant safety. Therefore, adherence to the criteria as specified in the Protocol is essential. Prospective approval of Protocol deviations to recruitment and enrollment criteria, also known as Protocol waivers or exemptions, are not permitted.

5.1. Inclusion Criteria

Participants are eligible to be included in the study only if all of the following criteria apply:

1. Male and female children aged ≥ 2 years to < 12 years (at the screening visit).
2. Diagnosis of AD as defined by the Hanifin and Rajka (1980) criteria.
3. AD duration of at least 3 months (participant/parent/guardian may verbally report signs and symptoms of AD with onset at least 3 months prior).
4. IGA score of 2 to 3 at the screening and baseline visits.
5. %BSA (excluding the scalp) with AD involvement of 3% to 20% at the screening and baseline visits.
6. For children aged 6 years to < 12 years, baseline itch NRS score ≥ 4 (see Section 8.2.7).
Note: Participants who are aged 6 years to < 12 years must record Itch NRS scores for at least 4 of the 7 days immediately prior to the Day 1/baseline visit.
7. Participants/guardians who agree to discontinue all agents used by the participant to treat AD from the screening visit through the final safety follow-up visit.
8. For participants who sign photography consent, at least 1 target lesion that measures at least 5 cm² at the screening and baseline visits. The target lesion must be representative of the participant's disease state but not located on the hands, feet, or genitalia.

9. For sexually active participants, willingness to take appropriate contraceptive measures (see [Appendix A](#)) to avoid pregnancy or fathering a child for the duration of study participation with the exception of male and female participants who are prepubescent.

Note: Female participants who have reached menarche must have a negative urine pregnancy test at the screening and baseline visits before the first application of study cream on Day 1. They must also take appropriate precautions to avoid pregnancy from the screening visit through the safety follow-up visit.

10. Ability to comprehend and willingness to sign an ICF or written informed consent of the parent(s) or legal guardian and a verbal or written assent from the participant when possible.

5.2. Exclusion Criteria

Participants are excluded from the study if any of the following criteria apply:

1. An unstable course of AD (spontaneously improving or rapidly deteriorating) as determined by the investigator over the previous 4 weeks before the baseline visit.
2. Concurrent conditions and history of other diseases as follows:
 - a. Immunocompromised (eg, lymphoma, acquired immunodeficiency syndrome, Wiskott-Aldrich syndrome) or a history of malignant disease within 5 years before the baseline visit.
 - b. Chronic or acute infection requiring treatment with systemic antibiotics, antivirals, antiparasitics, antiprotozoals, or antifungals within 2 weeks before the baseline visit.
 - c. Active acute bacterial, fungal, or viral skin infection (eg, herpes simplex, herpes zoster, chicken pox, clinically infected AD, impetigo) within 1 week before the baseline visit.
 - d. Any other concomitant skin disorder (eg, generalized erythroderma such as Netherton syndrome), pigmentation, or extensive scarring that in the opinion of the investigator may interfere with the evaluation of AD lesions or compromise participant safety.
 - e. Presence of AD lesions only on the hands or feet without prior history of involvement of other classic areas of involvement such as the face or the flexural folds.
 - f. Other types of eczema.
 - g. Chronic asthma requiring more than 880 µg/day of inhaled budesonide or equivalent high dose of other inhaled corticosteroids.
 - h. Any participant on maintenance dialysis.
 - i. A medical history of hepatitis B virus or hepatitis C virus infection.
3. Any of the following clinical laboratory test results at screening:
 - a. Removed during Protocol Amendment 2.
 - b. Removed (modified and moved to Exclusion Criterion 3d) during Protocol Amendment 2.
 - c. Cytopenias at screening, defined as follows:
 - Hemoglobin < 10 g/dL
 - ANC < 1000/µL
 - Platelet count < 100,000/µL

- d. Liver function tests:
 - AST or ALT $\geq 2.5 \times$ ULN
 - Total bilirubin $> 1.5 \times$ ULN (isolated bilirubin $> 1.5 \times$ ULN is acceptable if bilirubin is fractionated and direct bilirubin is $< 35\%$)
- e. Estimated GFR < 30 mL/min/1.73 m² (using the Modification of Diet in Renal Disease equation).
- f. Positive serology test results at screening for HIV antibody.
- g. Any other clinically significant laboratory result that, in the opinion of the investigator, poses a significant risk to the participant.

4. Removed (moved to Exclusion Criterion 2i) during Protocol Amendment 2.

5. Any serious illness or medical, physical, or psychiatric condition(s) that, in the investigator's opinion, would interfere with full participation in the study, including administration of study cream and attending required study visits; pose a significant risk to the participant; or interfere with interpretation of study data.

6. Use of any of the following treatments within the indicated washout period before the baseline visit:

- a. 5 half-lives or 12 weeks, whichever is longer – biologic agents (eg, dupilumab).
- b. 4 weeks – systemic corticosteroids or adrenocorticotropic hormone analogues, cyclosporin, methotrexate, azathioprine, or other systemic immunosuppressive or immunomodulating agents (eg, mycophenolate or tacrolimus).
- c. 2 weeks – immunizations with live-attenuated vaccines; sedating antihistamines unless on a long-term stable regimen (nonsedating antihistamines are permitted).
Note: Live-attenuated vaccines are not recommended during the VC period.
Note: COVID-19 vaccination is allowed.
- d. 1 week – use of topical treatments for AD (other than bland emollients, eg, Aveeno[®] creams, ointments, sprays, soap substitutes), such as topical antipruritics (eg, doxepin cream), corticosteroids, calcineurin inhibitors, PDE4 inhibitors, coal tar (shampoo), topical antibiotics, or antibacterial cleansing body wash/soap.
Note: Diluted sodium hypochlorite "bleach" baths are allowed as long as they do not exceed 2 baths per week and their frequency remains the same throughout the study.

7. Previous treatment with systemic or topical JAK inhibitors (eg, ruxolitinib, tofacitinib, baricitinib, filgotinib, lesartan, pacritinib).

8. Ultraviolet light therapy or prolonged exposure to natural or artificial sources of UV radiation (eg, sunlight or tanning booth) within 2 weeks prior to the baseline visit and/or intention to have such exposure during the study, which is thought by the investigator to potentially impact the participant's AD.

9. Removed (moved to Exclusion Criterion 3f) during Protocol Amendment 2.

10. Current treatment or treatment within 30 days or 5 half-lives (whichever is longer) before the baseline visit with another investigational medication or current enrollment in another investigational drug protocol.

11. Removed during Protocol Amendment 4.

12. In the opinion of the investigator, unable or unlikely to comply with the administration schedule and study evaluations.
13. Employees of the sponsor or investigator or otherwise dependents of them.

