8.4.3. Vital Signs, Height, and Weight

Vital signs, height, and weight will be measured as outlined in the SoA (see [Table 3](#) [VC period] and [Table 4](#) [LTS period]).

Vital sign measurements (to be taken before blood collection for laboratory tests) include blood pressure, pulse, respiratory rate, and body temperature. Blood pressure and pulse will be taken with the participant in the sitting position after 5 minutes of rest. Abnormal vital sign results identified after the first application of study cream constitute an AE if they are considered clinically meaningful, induce clinical signs or symptoms, or require concomitant therapy.

Height and weight will be assessed at the baseline, Week 8/ET, Week 24, and Week 52/EOT/ET visits. Individual growth measurements from the preceding year should be collected, if at all possible, from each participant's physician prior to the baseline visit. If these measurements cannot be obtained, the reason should be documented. Height will be measured using a stadiometer. The stadiometer should be calibrated, and a wall-mounted one is recommended. Participants should be measured without socks and 3 measurements taken to the nearest 0.1 cm. The average of the 3 height measurements of individual participants should be entered into the EDC. At the end of the study, these growth measurements will be compared against each participant's growth measurements from the previous year prior to entry into this trial.

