Rationale for change: Exclusion Criteria 2 were revised for updates and clarification; Exclusion Criteria 3 were revised, added, or moved to be consistent with exclusion criteria from other AD protocols. In addition, original Exclusion Criteria 3a and 3b were overly restrictive; Exclusion Criterion 3d was revised to group the 2 liver function tests for clarity; and Exclusion Criterion 3e, per recommendation by Canada Health Authorities, was revised to provide a more conservative estimated GFR value.

4. Section 6.5.1, Criteria and Procedures for Application Interruptions and Adjustments of Study Drug (Table 9: Guidelines for Interruption and Restarting of Treatment Applications if Adverse Event Is Deemed Related to the Study Drug)

Description of change: Deleted ALT and AST ($> 3 \times \text{ULN}$), revised ANC to $< 750/\mu\text{L}$ (without fever) and $< 1000/\mu\text{L}$ (with fever), and updated AST or ALT (from > 5 to $> 20 \times \text{ULN}$).

Rationale for change: To provide a more succinct guideline because ALT and AST $> 3 \times \text{ULN}$ is covered by "any other Grade 3 or higher laboratory abnormality" assessment, to define ANC levels with fever or without fever, and to update AST or ALT to $> 20 \times \text{ULN}$ to be consistent with CTCAE v5.0 grading.

5. Section 6.6.2, Restricted Medications and Procedures; Section 6.6.3, Prohibited Medications and Procedures

Description of change: Moved allergen immunotherapy and live-attenuated vaccinations from prohibited medications to restricted medications.

Rationale for change: Allergen immunotherapy and immunizations with a live-attenuated vaccine are standard of care for this pediatric population and therefore may be allowed during the VC period should the investigator deem it necessary.

6. Appendix C, COVID-19 Pandemic Mitigation Strategies and Instructions (Study Visits)

Description of change: [REDACTED]

Rationale for change: Administrative error.

7. Incorporation of administrative changes. Other minor, administrative changes have been incorporated throughout the Protocol and are noted in the redline version of the amendment.

Amendment 1 (06 MAY 2021)

Overall Rationale for the Amendment:

The primary purpose of the amendment is to incorporate revisions requested by the Canadian Health Authority and to address European regulatory requirements. Additional changes are summarized below.

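### Exclusion criterion 3e applies the MDRD equation to children aged 2 to under 12 without justification, so its cutoff of 30 acts well below 30 in younger children

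*Protocol*

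**What the plan says.** Protocol Section 5.1, criterion 1 ("Male and female children aged"), sets the age range at 2 to under 12 years at screening. Section 5.2, criterion 3e, excludes on a screening eGFR below 30 mL/min/1.73 m², obtained "using the Modification of Diet in Renal Disease equation". No coefficients, paediatric adaptation or reason for the choice are given.

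Three other criteria in Section 5.2 bear on renal disease:
- 2h: "Any participant on maintenance dialysis".
- 3g: "Any other clinically significant laboratory result that, in the opinion of the investigator, poses a significant risk to the participant".
- 5: serious illness that, in the investigator's opinion, poses a significant risk.

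The Appendix F log is used here only for intent. Under Amendment 2 the cutoff moved from below 15 to below 30, with the rationale that "Exclusion Criterion 3e, per recommendation by Canada Health Authorities, was revised to provide a more conservative estimated GFR value".

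Creatinine is a required analyte (Table 11) and serum chemistry is drawn at screening (Table 3). Height is not scheduled at screening: "Height and weight will be assessed at the baseline, Week 8/ET, Week 24, and Week 52/EOT/ET visits". Table 3 schedules the inclusion/exclusion check at both screening and Day 1.

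**The concern.** The standard MDRD equation uses creatinine, age and sex. Small children have low creatinine because they are small, and a height-based paediatric equation corrects for that. MDRD does not, and its negative power of age raises the result further at single-digit ages. A young child with substantially reduced renal function can therefore return an MDRD value far above 30.

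Criterion 3e is the only numerical renal threshold among the exclusions, and Section 5 bars waivers, so sites must apply it as written. At least 40% of participants are to be aged 2 to 6 (Section 4.1), where the discrepancy is largest. At stake is whether an objective safety criterion works at its stated value. Power, endpoints and treatment estimates are not affected.

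Other measures in the plan are adapted to age: the EASI multipliers (Appendix E), the BSA guides (Appendix D) and the vital-sign limits (SAP Section 9.5). The eGFR equation is not.

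**Working it through.** The cutoff of 30 is a chosen value, so there is no plan figure to reproduce. The check asks what height-based eGFR a child has when MDRD equals 30.

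**From the documents:** cutoff 30, MDRD, ages 2 to under 12.

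**Assumed, not in the documents:**
- MDRD = 175 × Scr^(−1.154) × age^(−0.203), × 0.742 if female, Scr in mg/dL. Alternatives: coefficient 186; a race multiplier of 1.212.
- Height-based eGFR = k × height (cm) / Scr, with k = 0.413. Alternative: k = 0.55.
- Mid heights of 87, 102, 115, 128, 138 and 149 cm at ages 2, 4, 6, 8, 10 and 11.9, varied by about 8 to 9% either way.

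**Step 1. Creatinine at which MDRD = 30:** Scr = [175 × age^(−0.203) × sex factor / 30]^(1/1.154).
Boy aged 2: 2^(−0.203) = 0.869; 175 × 0.869 = 152.0; 152.0 / 30 = 5.07; 5.07^0.867 = 4.08 mg/dL.

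**Step 2. Height-based eGFR at that creatinine:** 0.413 × 87 / 4.08 = 8.8.

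All ages, boy/girl, no race term, mid heights:

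| Age | Scr where MDRD = 30 (mg/dL) | Height-based eGFR, k = 0.413 | Height-based eGFR, k = 0.55 |
|---|---|---|---|
| 2 | 4.08 / 3.15 | 8.8 / 11.4 | 11.7 / 15.2 |
| 4 | 3.61 / 2.79 | 11.7 / 15.1 | 15.5 / 20.1 |
| 6 | 3.36 / 2.60 | 14.1 / 18.3 | 18.8 / 24.4 |
| 8 | 3.20 / 2.47 | 16.5 / 21.4 | 22.0 / 28.5 |
| 10 | 3.07 / 2.37 | 18.5 / 24.0 | 24.7 / 32.0 |
| 11.9 | 2.98 / 2.30 | 20.6 / 26.7 | 27.5 / 35.6 |

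**Step 3. The reverse, k = 0.413.** MDRD value (boy/girl) for a child at a given height-based eGFR:

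| Age | Height-based 30 | Height-based 15 |
|---|---|---|
| 2 | 123 / 92 | 55 / 41 |
| 6 | 72 / 53 | 32 / 24 |
| 11.9 | 46 / 34 | 21 / 15 |

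A 2-year-old at height-based 15 is not excluded by 3e; a boy aged 6 is borderline; an 11-year-old is excluded.

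**Step 4. Range.** With coefficient 175 and k = 0.413, varying height and the race term, the effective cutoff runs from 6.9 to 29.1 over all ages. Through age 6, with either coefficient, either k, heights ±9% and no race term, the highest value is 26.5. A race multiplier above 1 would lower the effective cutoff further.

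**The case against.** The strongest objection is that the whole calculation uses inputs from outside the documents, and that the result depends on them. This is partly right. With k = 0.55 the effective cutoff reaches 32.0 in a 10-year-old girl and 35.6 just under age 12, so the gap closes there. For the youngest it does not: a 2-year-old boy is still at 11.7.

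A reader might infer that 3e excludes almost no child with severe renal impairment. The figures do not support that. At k = 0.413 the effective cutoff at age 8 is 16.5/21.4, so 3e still covers 55% to 71% of the 0 to 30 interval (16.5/30 and 21.4/30). Just under age 12 it covers 69% to 89% (20.6/30 and 26.7/30). These are shares of the interval, not of children.

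Nor is 3e the only renal safeguard. Dialysis is excluded outright by 2h, and an investigator who sees a creatinine of 2 to 4 mg/dL can exclude under 3g or 5 whatever MDRD returns. That stands as mitigation. It is discretionary, however, and an MDRD result of 70 to 120 could falsely reassure.

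A reader might also infer that the cutoff contradicts the amendment's purpose. It does not: moving from 15 to 30 is more conservative under any equation, and the log does not show whether the authority considered the equation. What can be said is that in the youngest children the effective cutoff lies at or below the superseded 15 under the main assumptions.

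Finally, the documents do not show harm. Section 2.3.2 raises a possibility of higher plasma levels in younger children but ties it to the ratio of surface area to body mass, and nothing links renal function to exposure from the cream.

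**Conclusion.** The concern holds in a limited form. Criterion 3e uses MDRD in a population wholly under 12, with no justification in the protocol. Under coefficient 175, k = 0.413 and mid heights, its nominal 30 acts at a height-based eGFR of about 9 to 11 at age 2, 14 to 18 at age 6 and 21 to 27 just under 12. The direction is robust through age 6 across the assumptions tried; in the oldest girls it depends on k.

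The stated cutoff is thus not delivered in younger children, although the amendment aimed to be more conservative. Few children are likely to be affected, criteria 2h, 3g and 5 partly mitigate, and no efficacy analysis changes. It is worth correcting as an inexpensive repair to a safety criterion.

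**What to change.** Keep the sponsor's threshold in 3e and reconcile the equation with the enrolled age range by naming an eGFR equation suited to children, for example a height-based one, with its coefficients written out. If MDRD is to stay, state why it is adequate at ages 2 to under 12.

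No added screening measurement is required. The screening creatinine can be combined with the Day 1 height and the result confirmed at the Day 1 inclusion/exclusion check, before the first application. Because criterion 3 now refers to results at screening, 3e should say that this one is completed on Day 1.

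The cost is a wording change in 3e and a line in the site instructions. The downside is a rare extra screen failure, or one found on Day 1 instead of at screening.

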5.3. Lifestyle Considerations

Prolonged exposure to natural or artificial sources of UV radiation (including sun lamps, tanning booths, etc) is prohibited from 2 weeks prior to the baseline visit through the last study visit. When outdoors, participants will be advised to wear loose-fitting clothing that protects the treated areas from the sun.

If sunscreen, makeup, or other cosmetics have been applied to the areas to be treated, participants should wash the treatment areas with mild soap and water and pat dry before application of study cream. See Section [6.6.1](#) for additional guidance.

Participants should abstain from physical activity that can cause significant sweating for approximately 2 hours following study cream application.

Use of swimming pools during the VC period of the study is not recommended. If unavoidable, it is recommended that swimming should not take place within 2 hours before and after study cream application.

5.4. Screen Failures

Screen failures are defined as participants who consent to participate in the clinical study but are not subsequently entered into the study.

Tests with results that fail eligibility requirements may be repeated once during screening if the investigator believes the result to be in error. Additionally, a participant who fails screening may repeat the screening process 1 time if the investigator believes that there has been a change in eligibility status. Participants who rescreen must reconsent (if rescreened \geq 28 days after the initial screening or \geq 35 days after the initial screening for those participants on prior medications requiring a 4-week washout period, as described in Section [5.2](#), Exclusion Criterion 6b) and be assigned a new screening number.

5.5. Replacement of Participants

Participants are not anticipated to be replaced during the study. However, as noted in [Appendix C](#) (COVID-19-related guidance), due to the evolving situation of the COVID-19 pandemic, the sponsor may decide to recruit additional participants in the study beyond the expected number (eg, if a substantial number of participants withdraw early from the study).

6. STUDY TREATMENTS

See [Appendix C](#) for COVID-19-related guidance.

6.1. Study Treatments Administered

[Table 8](#) presents the study treatment information.

Table 8: Study Treatment Information

	Study Treatment 1	Study Treatment 2	Study Treatment 3
Study treatment name:	Ruxolitinib cream 1.5%	Ruxolitinib cream 0.75%	Vehicle
Treatment strength:	1.5%	0.75%	Not applicable
Mechanism of action:	Inhibitor of the JAK family of protein tyrosine kinases	Inhibitor of the JAK family of protein tyrosine kinases	Not applicable
Dosage formulation:	Cream		
Route of administration:	Topical		
Administration instructions:	VC period: BID (morning and evening applications at least 1 hour before bedtime); a thin film is applied to affected areas. LTS period: BID (morning and evening applications at least 1 hour before bedtime); a thin film is applied to affected areas.		
Packaging and labeling:	Ruxolitinib cream and vehicle cream will be provided in 60-g tubes. Each tube will be labeled as required per country requirements.		
Storage:	Ambient (15°C-30°C/59°F-86°F)		
Status of treatment in participating countries:	Investigational	Investigational	Not applicable

Study treatments (ruxolitinib cream 1.5%, ruxolitinib cream 0.75%, and matching vehicle cream formulation that does not contain active drug) will be supplied in 60-g tubes and applied topically as a thin film BID (optimally at equal intervals, eg, ideally 12 hours apart but with at least 8 hours between applications) to the affected areas in the morning and in the evening, with the evening application at least 1 hour before bedtime.

At the baseline visit, an estimate of the %BSA to be treated will be used by the IRT system to calculate the number of tubes of study cream to be dispensed. All areas identified at the baseline visit should continue to be treated through the end of the VC period (at Week 8), even if the area begins to improve or the AD resolves completely, unless the participant meets criteria for stopping study cream.

If there are new areas to be treated, including expansion of existing areas or development of new areas, after consultation with the investigator, study cream should be applied to these areas in addition to the areas identified at the baseline visit (up to 20% BSA) for the remainder of the VC period, and the percentage of BSA to be treated will be recalculated and increased. This new estimate will be entered into the IRT system to calculate the number of tubes of study cream to be dispensed. Approval to treat these additional areas may occur via telephone, although the investigator, at their discretion, may ask the participant to return for an unscheduled visit. This is a close reflection of the clinical practice of managing AD in the outpatient setting. Participants

whose additional new areas to be treated in addition to the areas identified at the baseline visit exceed 20% BSA should be discontinued from study treatment and complete the EOT assessments.

During the LTS period starting at the Week 8 visit, participants will have study visits every 4 weeks until the end of the study (44 weeks total). At those visits, AD lesions will be evaluated by the investigator to confirm whether the participant still requires continuation of therapy (IGA score ≥ 1) or can otherwise (re)enter the observation/no treatment cycle (IGA score = 0). During this period, only areas with active disease need to be treated. Participants who develop new or expanded areas of AD may treat these additional areas with approval by the investigator as long as the total treated BSA does not exceed 20% and there are no safety concerns regarding the additional application of study cream. At Week 8, each participant will receive a prespecified number of tubes of study cream corresponding to a lower %BSA affected (up to 5%) or higher number of tubes corresponding to their affected %BSA ($> 5\%$). This new estimate will be entered into the IRT system to calculate the number of tubes of study cream to be dispensed.

The start and end dates of treatment applications will be captured by the participant. Once the lesions clear, participants should continue to apply study cream for an additional 3 days to the areas of the body where lesions were last present before discontinuing treatment. If this 3-day window is during a study visit and the IGA score is 0, as assessed by the investigator, treatment is to be stopped. The date of the study visit will be recorded as the treatment cycle end date. If a lesion recurs, then treatment should be resumed at the first sign of recurrence.

At any time during the LTS period, if a participant's new areas to be treated in addition to the areas identified at the previous visit exceed 20% BSA, then the participant should be discontinued from study treatment and complete the EOT assessments.

No study treatment adjustments are allowed except for temporary drug discontinuation, if needed (eg, for management of an AE; see Section 6.5).

